14.4 Audiometric Assessments

Change in audiometric measurements (shifts) from baseline to each follow-up visit for subjects in the Safety Analysis Set will be presented using descriptive statistics (mean, SD, median, minimum and maximum). Shifts in air conduction (AC) and bone conduction (BC) hearing thresholds will be reported for each frequency (500, 1000, 2000 and 4000 Hz) on a by-ear basis, and for each treatment arm in Group A (active or sham treatment). Shifts from baseline to each follow-up visit in air-bone gap (air conduction minus bone conduction) will also be reported for each frequency (500, 1000, 2000 and 4000 Hz) on a by-ear basis, and for each treatment arm in Group A. Shifts in air conduction pure tone average (AC PTA), bone conduction PTA (BCA) and air-bone gap averages will be presented for each follow-up time point by ear for each Group and by treatment. For all PTA measurements, the PTA will be calculated by adding the threshold levels in decibels (dB) obtained at each frequency tested divided by number of frequencies tested.

Shift tables for air conduction pure tone averages greater than 15 dB (>15dB) by ear will be calculated, and presented by ear for each Group and by treatment for each follow-up time point.

Degree of hearing loss severity will be defined according to the protocol (slight through profound) and presented by subject for each Group and by relationship to study device, procedure or study drug.

14.5 Tympanometry

Tympanometry results are used to assess of tube patency (for Group B only) and for changes in middle ear condition. Tympanometry will be performed for both ears for all subjects (Groups A and B) at screening and at all follow-up visits. The number and percentage of ears in each Group with tympanogram types A, B or C will be presented for all subjects and for each treatment arm (sham or active treatment in Group A) in the Safety Analysis Set at screening and all follow-up time points.

14.6 Otoscopic Assessments

Otoscopic examination will be performed in all ears intended for treatment at all protocol-defined time points. The number and percentage of ears in each Group with abnormal findings for the external acoustic meatus or tympanic membrane will be presented for all subjects in the Safety Analysis set for screening and all follow-up time points.

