Group B subjects will receive active lidocaine iontophoresis and will have tubes placed using the TDS in all ears indicated for tube placement. The subject will rate the pain upon TDS tube insertion using the VAS, and the pain score will be compared to a performance goal. [REDACTED]

[REDACTED]
[REDACTED]
[REDACTED]
[REDACTED] Vital signs (diastolic and systolic blood pressure, heart rate, respiratory rate and pulse oximetry) will be monitored prior to and periodically up to 1 hour following iontophoresis. A follow-up at 3 weeks is required for all subjects, at which point otologic examination, cranial nerve physical exam, tympanometry and audiometry will be conducted.

Study Design:	Study Phase: Pre-Pivotal
	Group A: No. of Centers: 2 Number of Arms: Randomized (1:1), double-blind, sham-controlled design with two arms (active lidocaine iontophoresis vs sham lidocaine iontophoresis) Enrollment: 40 healthy adult subjects
	Group B: No. of Centers: up to 9 Number of Arms: Single arm Enrollment: 30 adult subjects requiring tympanostomy tubes
Safety Evaluations	Safety Evaluation will include the following assessments: 
 • Otoloscopic examination for visual inspection of external ear canal and TM condition at baseline, post-procedure and at the follow-up visit(s). The post-procedure exam also includes an examination of the myringotomy wound and tympanostomy tube for Group B subjects. • Audiometry to assess hearing at baseline and at the follow-up visit(s). • Tympanometry to assess tympanic membrane, middle ear conditions and tube function (Group B only) at baseline and at the follow-up visit(s). • Cranial nerve physical exam to assess cranial nerve function at baseline, post-procedure (Group B only) and at the follow-up visit(s). • Vital signs (blood pressure, oxygen saturation, respiratory and heart rates) prior to and up to one-hour following iontophoresis (Group B only). • Adverse events
Endpoints:	Primary Endpoints: Group A 
 • Anesthesia Effectiveness: Subject-reported pain score elicited by tympanic membrane tap following active lidocaine iontophoresis compared to sham lidocaine iontophoresis using the VAS. Group B 
 • Tube Placement Tolerability: Subject-reported pain score following TDS tube placement using the VAS by subject compared to a performance goal.
	Secondary Endpoints: None

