11.9. Inclusion Criteria

Group A: At least one ear must meet ear-specific eligibility criteria.

Group B: Each ear indicated for tube placement must meet ear-specific eligibility criteria.

Group A:

1. Healthy adults, 18-50 years old at time of consent
2. Subject is able and willing to comply with the protocol and attend all study visits
3. Subject is able and willing to provide informed consent
4. Subjects with air conduction hearing thresholds of 25 dB HL or better at standard frequencies up to 2000 Hz, and 45 dB or better at 4000 Hz.
5. Subject is able to read and understand English

Group B:

1. Adults at least 18 years of age at time of consent
2. Indication for tympanostomy tube insertion per Clinical Practice Guideline,⁴⁰ or indicated for tympanostomy tube insertion due to barotrauma or Eustachian tube dysfunction per AAO-HNS Clinical Indicators⁴¹
3. Subject is able and willing to comply with the protocol and attend all study visits
4. Subject is able and willing to provide informed consent.
5. Subject is able to read and understand English.

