12.2.4. Otoscopy

An otoscopic exam will be conducted for both ears in all subjects for all study visits. The otoscopic examination will be used to visually examine the condition of the external ear canal and TM. Routine ear cleaning may be conducted only to the extent necessary to ensure the tympanic membrane and ear canal are free from matter that may interfere with iontophoretic delivery and to ensure visualization of the tympanic membrane.

The exam will be used to confirm eligibility and to assess the ear canal and TM for changes or adverse effects. Presence or absence of middle ear effusion will be assessed. In addition,

appearance of the myringotomy wound and patency of the tympanostomy tube (Group B only) will be evaluated at the follow-up visit. Tube functional patency will be determined through clinical assessments including otoscopic examination and tympanometry.

The screening otoscopic exam may be conducted up to 28 days prior to procedure and will be conducted for both ears of all subjects to determine eligibility and ears selected (Group A) or indicated (Group B) for treatment. Otosopic examination is considered standard of care for the Group B patient population and may be obtained prior to study informed consent as a screening assessment within 28 days prior to procedure. Otosopic images may be collected prior to and following iontophoresis.

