12.5.2. Otoscopic Examination and Ear Preparation

An otoscopic exam will be conducted using a microscope for all ears planned for treatment for subjects in Groups A and B prior to procedure. The otoscopic examination will be used to visually examine the condition of the external ear canal and TM. Routine ear cleaning may be conducted, if needed, only to the extent necessary to ensure the tympanic membrane and ear canal are free from matter that may interfere with or influence the evaluation and to ensure visualization of the tympanic membrane. Changes in concomitant medications will be recorded.

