12.7. Group B Follow-up

3-Week Post-Procedure Follow-Up Visit (+/- 7 Days)

1. All subjects are required to return for the 3-week post-procedure follow-up visit.
2. An otoscopic examination will be used to visually examine the condition of the external ear canal, TM, myringotomy wound and tube patency.

3. The subject will complete audiometry and tympanometry, and cranial nerve physical exam.
4. Subjects will be evaluated for any adverse events, and changes in concomitant medications will be recorded.
5. The subject will then be exited from the study

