23.0 Definition of Variables

23.1 Baseline

Baseline is defined as the last observation recorded prior to the treatment procedure.

Age will be calculated in years and fractions of year based on the date of informed consent relative to date of birth.

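### SAP 14.6 reports otoscopy as percent abnormal per visit, so for Group B tympanic membranes it cannot separate new or worsened findings from entry disease and the intended tube

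*SAP*

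**What the plan says.** - **SAP 14.6** sets the otoscopy output: "The number and percentage of ears in each Group with abnormal findings for the external acoustic meatus or tympanic membrane will be presented", "for screening and all follow-up time points". It has no category for new, worsened or shifted findings. It does not say whether canal and membrane get separate rows, or whether a tube in place counts as abnormal. No split by Group A arm is stated.
- **Protocol 12.2.4** gives the purpose: "The exam will be used to confirm eligibility and to assess the ear canal and TM for changes or adverse effects".
- **SAP 23.1**: "Baseline is defined as the last observation recorded prior to the treatment procedure". **Protocol 12.5.2** supplies such an observation on the procedure day: "An otoscopic exam will be conducted using a microscope for all ears planned for treatment".
- **Protocol 5.0** (safety evaluations) places otoscopy at baseline, after the procedure and at follow-up. SAP 14.6 does not name the post-procedure exam among the tabulated visits.
- **Protocol 11.9** admits Group B ears through "Indication for tympanostomy tube insertion per Clinical Practice Guideline", or through barotrauma or Eustachian tube dysfunction. At 3 weeks, **Protocol 12.7** has the examiner "visually examine the condition of the external ear canal, TM, myringotomy wound and tube patency".
- **Neighbouring SAP sections** differ. 14.4 (audiometry) uses shifts by ear and 14.7 (cranial nerves) uses change from baseline. 14.5 (tympanometry) uses percentages per visit by tympanogram type. 14.4 and 14.5 both split Group A by arm.

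**The concern.** The protocol wants otoscopy to detect change, but the SAP reports two separate percentages. These give the net difference between visits. They do not show how many ears developed a new finding, because ears that resolve offset ears that deteriorate.

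For Group B membranes this matters more, because both columns have a reason to be high that has nothing to do with injury. At screening the ear may show the disease that led to the tube indication. At 3 weeks it has had a myringotomy and should hold a tube. A membrane that was abnormal at entry and got worse counts once at each visit, exactly like one that stayed the same.

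The reference column adds to this. Screening otoscopy may be up to 28 days old (Protocol 12.2.4), and the closing text of Protocol 11.10 foresees ears whose condition has changed by the procedure day. A change that came before the procedure would then appear as a difference at follow-up.

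At stake is how well the otoscopy table serves as a systematic cross-check on adverse event reporting for the safety part of the second objective.

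**Working it through.** The plan states no figure for this table, so there is nothing to reproduce. The check asks what the planned percentages can reveal about newly abnormal ears.

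**Inputs**
- Group B has 30 evaluable subjects treated in one or both ears (SAP 4.0), hence 30 to 60 treated ears. The unilateral/bilateral split is not given. I use 45 for illustration: 15 unilateral and 15 bilateral subjects give 15 + 2 × 15 = 45.
- The documents give no rate of abnormal otoscopy at any visit. All rates below are assumptions.

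**Formula.** Let n be the number of ears, a the number abnormal at screening and b the number abnormal at follow-up. The number of ears that go from normal to abnormal is only known to lie between max(0, b − a) and min(b, n − a) (Fréchet bounds).

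| n | a | b | Lowest | Highest |
|---|---|---|---|---|
| 45 | 0 | 9 | 9 | 9 |
| 45 | 4 | 9 | 5 | 9 |
| 45 | 36 | 36 | 0 | 9 |
| 45 | 36 | 45 | 9 | 9 |
| 45 | 45 | 36 | 0 | 0 |

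**Reading the rows**
1. No ear abnormal at screening: the follow-up count is the number of new findings. This is roughly the situation for conditions excluded at entry.
2. About 10% abnormal at screening and 20% at follow-up: the range is 5 to 9, which is still informative.
3. 80% abnormal at both visits: max(0, 36 − 36) = 0 and min(36, 45 − 36) = 9, so 0 to 9 of 45 ears (0 to 20%). With 30 ears (24 and 24) the range is 0 to 6, and with 60 ears (48 and 48) it is 0 to 12. The upper end is 20% each time.
4. 80% at screening and every ear abnormal at follow-up, as would happen if the tube itself were coded abnormal: the count is exactly 45 − 36 = 9. That is only the number of ears that entered normal, and it says nothing about injury.
5. Every ear abnormal at screening: no ear can become newly abnormal on a yes/no scale, whatever happens to it.

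In every row, worsening within an ear that was already abnormal is not bounded at all. A within-ear cross-table of baseline against follow-up would replace each range with a count. Grading or typing the findings would also show worsening.

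**The case against.** The case against giving this much weight is strong, and most of it stands.

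- **The adverse event route covers injury.** The safety endpoint is the occurrence of adverse events. Protocol 13.1 counts clinically significant changes found at protocol evaluations, and applies a worsening rule to pre-existing conditions. SAP 14.1 tabulates events by relationship to device, procedure and drug. Protocol 13.5 has ear-related events reviewed within 24 hours of sponsor awareness. SAP 22.0 lists all eCRF data per subject.
- **Entry exclusions help.** Protocol 11.10 excludes Group B ears with perforation, otitis externa, hemotympanum or damaged canal skin. Follow-up counts of those should be close to counts of new findings, provided they can be read separately.
- **SAP 14.6 is not alone.** SAP 14.5 also gives percentages per visit, though by type and not in a single abnormal class.
- **Screening can be the procedure day** (Protocol 12.4), so the reference is not always old.
- **Redactions.** Parts of SAP 14.1 and the section before SAP 17.0 are blacked out, so further otoscopy summaries cannot be ruled out.

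A reader might infer that Group B device or procedure injury would go unseen, or that a cluster of new injuries would leave the abnormal percentage unmoved. The documents do not support either. The first ignores the adverse event tables, the listings and the exclusions. The second needs nearly all membranes abnormal at screening, canal and membrane pooled in one row, and a correctly placed tube counted as abnormal. None of these is stated, and Protocol 12.7 names wound and tube patency apart from canal and membrane.

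What the objection does not remove: adverse event recording depends on judging clinical significance and on setting aside natural history, which is hardest in a diseased ear. The listings hold the data but leave the reader to build the within-ear comparison by hand.

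**Conclusion.** The point holds as a weakness of one descriptive safety table. The planned summary does not measure change. For Group B membranes it cannot separate new or worsened findings from disease at entry and the intended result. With an assumed 80% abnormal at both visits, it leaves up to 20% of ears (0 to 9 of 45) undetermined. With low abnormality at screening the uncertainty shrinks or disappears, so the size depends on a rate that the documents do not give and on how a tube in place is coded. Safety data are not lost, and neither the two primary endpoints nor the adverse event endpoint is affected. The change is worth making because it is cheap and brings the table into line with the stated purpose of the exam.

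**What to change.** Amend SAP 14.6 to add a within-ear table of new or worsened otoscopic findings relative to the SAP 23.1 baseline, that is, the last exam before the procedure:

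- separate rows for ear canal and tympanic membrane, by type of finding;
- the expected tube and myringotomy coded apart from abnormal findings;
- the post-procedure exam named in Protocol 5.0 as well as the follow-up visits;
- Group A split by arm, as in SAP 14.4 and 14.5.

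The percentages per visit can stay alongside. The cost is SAP wording and one additional table. It uses exams that are already scheduled, with no new visits.

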14.7 Cranial Nerve Function

Cranial nerve function physical examination will be performed for all subjects at screening, post-procedure and at all follow-up visits. The change from baseline for subjects in the Safety Analysis set in each Group will be presented for all follow-up visits.

15.0 Prior and Concomitant Medications

Prior and concomitant medications including prescription and over-the counter drugs will be recorded for Groups A and B. Medications will be coded using the World Health Organization Drug Dictionary (WHO Drug) to identify the drug class and preferred drug name.

Concomitant medications will include all medications that started on or after the procedure through the final study follow-up visit. Prior medications will include all medications that started within 28 days prior and stopped prior to the day of procedure.

Prior and concomitant medication data will be presented in a data listing for safety subjects.

[REDACTED]

17.0 Handling of Missing Data

Missing data and the causes of the missing data will be summarized and presented. The number and proportion of subjects eligible for and compliant with all follow-up examinations will be presented. Subjects who withdraw from the study will be tabulated with the reasons for the withdrawal. Subjects who initiate the procedure, regardless of tolerability outcome or anesthesia effectiveness, will be encouraged to return for all follow-up assessments.

Group A Primary Endpoint: If a subject in Group A discontinues iontophoresis prior to the TM tap assessment or declines TM tap assessments, the subject will provide a VAS pain score for the attempted procedure and will be included in the analysis of the primary endpoint. [REDACTED]

[REDACTED]

[REDACTED] Reasons for discontinuation will be documented and presented in the clinical study report.

Group B Primary Endpoint: If a subject in Group B discontinues iontophoresis or tube placement, the subject will provide a VAS pain score for the attempted procedure. Subjects with discontinued procedures will be included in a sensitivity analysis, but will not be included in the primary analysis. Only subjects with VAS scores after tubes are successfully placed in all indicated ears (one tube placed if indicated for unilateral treatment and two tubes placed if indicated for bilateral treatment) will be included in the primary analysis. If a bilateral subject has successful tube placement for one ear, but the second ear is discontinued, the higher ('worst') VAS score will be used for the sensitivity analysis. [REDACTED]

[REDACTED] Reasons for discontinuation will be documented and presented in the clinical study report.

[REDACTED]

[REDACTED]

[REDACTED]

[REDACTED]

[REDACTED]

[REDACTED]

[REDACTED]

[REDACTED]

[REDACTED]

[REDACTED]

[REDACTED]

[REDACTED]

- [REDACTED]
- [REDACTED]
- [REDACTED]

[REDACTED]

- [REDACTED]
- [REDACTED]

[REDACTED]

[REDACTED]

[REDACTED]

[REDACTED]

[REDACTED]

[REDACTED]

[REDACTED]

[REDACTED]

21.0 Multiplicity Adjustment

Groups A & B each have a single primary endpoint tested at a significance level of 2.5%. Each primary endpoint must pass the statistical test for the study to be considered successful. The familywise error rate is therefore controlled at 2.5% and no multiplicity adjustments are planned.

22.0 Data Listings

Subject data will be summarized using listings and tables. All electronic case report form (eCRF) data will be listed per subject for all enrolled subjects. All listings will include the subject number and the identification of the study Group and treatment for Group A only.

23.0 Definition of Variables

23.1 Baseline

Baseline is defined as the last observation recorded prior to the treatment procedure.

Age will be calculated in years and fractions of year based on the date of informed consent relative to date of birth.

23.2 Study Day Calculation

Study Day 0 is the date of study procedure. Study Day is calculated relative to Study Day 0 and will appear in the listings where applicable.

Study Day will be calculated as:

$$\text{Study Day} = \text{Date of event} - \text{Date of study procedure}$$

Due to the acute nature of the study, no rules will be applied (eg, to assign missing day as 15th of month). Missing date data (day, month or year) will be queried.

24.0 Other General Considerations

Raw data will be presented with the exact precision that it was collected on the eCRF or other external data sources.

Percentages will be reported with exactly one decimal place. The mean and standard deviation as well as any corresponding confidence intervals will be reported with one decimal place. Blank fields on an eCRF will be displayed as blank fields in corresponding listings.

26.0 Appendix - Code
